Wearable for LC PIs: [name]; [name], PhD Mayo Clinic - NCT05199233

The primary outcome will be the adherence to the Muse-STM by summarizing the frequency of use and duration of use each time it was accessed.

The secondary outcomes will include:

o change in quality of life (QOL), stress, anxiety, and cognition, score over time

Background:

According to the CDC, new or ongoing symptoms of long COVID may include difficulty breathing or shortness of breath, tiredness or fatigue, difficulty thinking or concentrating, cough, chest and/or stomach pain, headache, heart palpitations, joint and/or muscle pain, pins and needles, diarrhea, sleep problems; all of which can increase anxiety and stress in the post-covid patient.

Integrative Medicine has introduced many mind-body therapies for addressing mental stress. The top stress relievers recommended by Mayo Clinic include: getting active, eating a healthy diet, avoiding unhealthy habits, meditation, laughing more, connecting with others, asserting yourself, practicing yoga, getting enough sleep, keeping a journal, exploring music and being creative, seeking counseling². Among all of these potential options, meditation is the easiest to incorporate in a current lifestyle yet most difficult to undertake without proper training and guidance at the beginning. Muse-STM is a clinical grade, headband-style wireless EEG system designed to interact with a mobile device (a smartphone or tablet) (https://choosemuse.com). In combination with the Muse-STM APP running on iOS or Android smartphones, Muse-STM converts EEG signals measured over the frontal and temporal cerebral cortices into measures of brain state. At the same time Muse-STM can also guide the user through the meditation steps. Calibrated to an individual user, Muse-STM distinguishes between active and calm brain states to provide real-time performance feedback, and helps users realize the benefits of mindfulness practice in an engaging and accessible manner. Muse-STM also has a PPG sensor that tracks heartrate during meditation sessions as well. This has been tested in a prior study by some of the current study team (SP and ITC), with patients undergoing breast cancer surgery³ and is currently being test in patients with fibromyalgia who concurrently experience pain (ITC and RG) and in healthcare providers who are under stress (ITC).

Study Design and Methods

Methods:

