All study participants will receive the Muse S^{TM} Headband system at study entry and will be asked to utilize it at least 4 times per week for a minimum of 10 minutes each time over a period of 3 months (12 weeks). They will be followed for a period of 6 months (3 months of treatment and 3 months post treatment) according to the schedule below.

We arable for LC

Pls: [name]; [name], PhD

Mayo Clinic - NCT05199233

	Consent /screen /baseline	Treatment Phase				Follow up Phase
Visit No.	1	2	3	4	5	6
Visit Type	Face to Face	Phone	Phone/ Email	Phone/ Email	Face to Face/ Phone/ Email	Face to Face/ Phone/ Email
Visit Days	0	2	30	60	90	180
Consent/Screening/						
Enrollment						
Informed Consent	X					
Inclusion/Exclusion	X					
Demographic and History	X					
Form	Λ					
Safety Data						
Depression	X		X	X	X	X
Adverse Events ¹			X	X	X	X
Concomitant Medication ²	X		X	X	X	X
Intervention						
Instructions for Muse-S TM & Fitbit [®] Tracker	X					
Muse-S TM use	X		X	X	X	
Fitbit [®] Tracker		X			X	X
Outcome						
CBS Cognitive Tests	X				X	X
Anxiety	X		X	X	X	X
Cognition Function	X		X	X	X	X
Emotional Distress	X		X	X	X	X
Quality of Life	X		X	X	X	X
Resilience	X		X	X	X	X
Self-Efficacy	X		X	X	X	X
Sleep	X		X	X	X	X
Stress Scale	X		X	X	X	X
Satisfaction Survey						X
End of Study Forms						X

^{1 =} For visit 5 & 6 only serious adverse events will be newly collected; 2 = For visit 5 & 6, only newly added concomitant medications will be collected

Study Visit Windows:

Each visit will have a window from the midpoint of the prior visit to the midpoint of the latter visit.

Data Collection:

Mayo Clinic - NCT05199233

Subjects will have the options of completing study surveys/questionnaires online via email link to REDCap prior to study visit. If not completed by the time the study visit takes place, the coordinator can provide the iPad digital version of the survey/questionnaire to the subject for the in-person visits or can interview the patient via phone for the telephone visits. If a subject misses a visit, the study staff will connect with the subject to collect what study data is appropriate through a simple virtual connection (email redcap surveys or telephone interview of surveys). Data Collection in this study will utilize REDCap⁴. All other data collection will be entered directly into a password protected system.

Assessments:

Safety:

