• Depression: The PHQ-2^{5,6} is a validated and frequently used self-report measure of depressive symptoms comprising of 2 questions, which were derived from the PHQ-9^{7,8}.

Outcomes:

- Demographics Form: This form collected demographic and other lifestyle history of the research subject.
- Quality of Life: Will be measured using the *Linear Analogue Self-Assessment (LASA)*⁹⁻¹¹. This is a six-item measure of quality of life (QOL), in which QOL is conceptualized as a multidimensional construct with five domains (physical, functional, emotional, spiritual, and social). This data will be collected at screen (prior to any treatment), day 30, day 60, day 90 end of treatment, and day 180 end of study (3 months post last treatment).
- Anxiety: State-Trait Anxiety Inventory (STAI-Y1)¹²⁻¹⁶ This 20-item self-report measure indicates the intensity of feelings of anxiety; it distinguishes between state anxiety (a temporary condition experienced in specific situations) and trait anxiety (a general tendency to perceive situations as threatening). It uses a 4-point visual analog scale, and the participant indicates how they feel in the moment (1 = not at all to 4 = very much so).
- Stress: Will be evaluated through the *Perceived Stress Scale (PSS)*^{17,18}. The PSS is a 10-item Likert scale that measures global life stress by assessing the degree to which experiences are appraised as uncontrollable or unpredictable. Scores can range from 0 to 40, with higher scores indicating greater perceived stress. Reliability is reported as 0.85, with Cronbach alphas ranging from 0.75-0.86.
- Resilience: Will be evaluated through the *Connor-Davison Resilience Scale 10 (CD-RS10)*¹⁹. This is a 10-item, Likert scale, validated scoring system. The CD-RS10 is a reliable means of assessing resilience and is most often used in medical and/or disaster studies²⁰.

Sleep Quality:

(ASCQ-Me® v2.0 Sleep Impact - Short Form²¹) is an effective instrument used to measure the impact sleep has on overall health in adults. The ASCQ-Me Sleep Impact SF is equivalent to the PROMIS Sleep Disturbance and Sleep-Related Impairment Surveys except the scoring is reversed.²¹ The PROMIS surveys indicate greater symptom burden as the score goes higher and the ASCQ-ME survey indicates better health as the score goes up. The Sleep Impact Scale consists of 5-item, likert scale, validated, scoring system.²² The 5 questions focus on experiences in the prior 7 days.

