Self-efficacy (Short Form 4a – 4 items)²³: This PROMIS Self-efficacy Scale defines self-efficacy as confidence in one's ability to successfully perform specific tasks or behaviors. It assesses confidence in one's ability to successfully perform specific tasks or behaviors related to one's health in a variety of situations. Each item on the measure is rated on a 5-point scale (1=I am not at all confident; 2=I am a little confident; 3=I am somewhat confident; 4=I am quite confident; 5=I am very confident)

Wearable for LC PIs: [name]; [name], PhD Mayo Clinic - NCT05199233

- Emotional Distress: Adapted from the Emotional Distress-short form 7a (7 items)²³. The PROMIS Anxiety item banks assess self-reported fear (fearfulness, panic), anxious misery (worry, dread), hyperarousal (tension, nervousness, restlessness), and somatic symptoms related to arousal (racing heart, dizziness). Anxiety is best differentiated by symptoms that reflect autonomic arousal and experience of threat. Only one behavioral avoidance item is included in the adult item bank; therefore, behavioral fear avoidance is not fully evaluated. The anxiety measures are universal rather than disease specific. The original adult short form (7a), which is being used in this study was constructed by the domain team with a focus on representing the range of the trait and also representing the content of the item bank. Domain experts reviewed short forms to give input on the relevance of each item. Psychometric properties and clinical input were both used and likely varied in importance across domains. Each item on the measure is rated on a 5-point scale (1=never; 2=rarely; 3=sometimes; 4=often; and 5=always) with a range in score from 7 to 35 with higher scores indicating greater severity of anxiety. The original form instructed participants to think about the past seven days, but for purposes of this study, we will reword the question to focus on the current time ('now').
- Cognitive Function (short form 6a 6 items)²³: The PROMIS Cognitive Function and Cognitive Function Abilities Subset item banks assess patient-perceived cognitive deficits. Facets include mental acuity, concentration, verbal and nonverbal memory, verbal fluency, and perceived changes in these cognitive functions. The extent to which cognitive impairments interfere with daily functioning, whether other people observe cognitive impairments, and the impact of cognitive dysfunction on quality of life are also assessed.

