Use of Muse-STM Headband systems will be demonstrated to each participant prior to their first mindfulness practice session, which will be completed during the baseline visit with the study coordinator. The study coordinator will present the participant with detailed instructions on how to begin each session. The frequency of the sessions thereafter will be at the participant's discretion according to the study's requirements (daily practice). Mindfulness training will follow the protocol in the Muse-STM

APP, which follows a standard breathing exercise with EEG brain state feedback through the mobile device, as designed by a panel of experienced mindfulness practitioners. In short, the Muse- S^{TM} functions like a $FitBit^{\textcircled{R}}$ like device for the brain.

The study participants can access 3 different types of meditation while using the Muse-STM Headband system. They are as follows:

Wearable for LC PIs: [name]; [name], PhD Mayo Clinic - NCT05199233

• Mind Meditation uses the Muse-STM headband to track the user's brain activity during meditation and translates the brain's activity into guiding sounds. This is a classic focused attention on the breath meditation, where you get real time feedback on your brain. Users get real time feedback to know when they are in focused attention and when their mind is wandering and are cued to return to a state of focused attention (meditation state). Users also see data from their brain after the meditation. Real time feedback during Mind Meditation is the Muse-STM signature meditation and teaches the fundamentals of a meditation practice in remaining in a calm focused attention state and being able to move your mind away from distracting thoughts. This teaches them the skill to notice their minds and learn to direct themselves out of their discursive mind and onto a neutral object like their breath, while giving them neurofeedback to guide them when they are "doing it right" and reinforce the learning. It is recommended that Muse Mind be done daily for a minimum of 5 minutes per day. Users can do more if they choose.

- **Guided Meditation** These are different breathing exercises where different breathing techniques, such as box breathing, 6-4 breathing, etc., are taught to help the individual regulate their breath. The participant is given real time feedback to keep them breathing along in time with the guide.

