Participants will be asked to wear their Fitbit® 24/7 except during a time of recharging. Fitbit® Data will be collected at visits 2, 5 and 6 by the study team and from participants Fitbit® app that has been downloaded on their personal electronic device. The data collected will include Heart Rate, steps, sleep quality, and blood oxygen saturation level (SpO₂).²⁹ A Fitbit® account will be created by each study participant with the help of the research coordinator to allow us to track study participation. Information collected from the Fitbit® app will be logged into the database. This approach for working with the Fitbit has been successfully used in the past by Mayo investigators.³⁰

Subject Retention:

Participants will not be remunerated for participating in this study, but they will be allowed to keep the Muse-STM Headbands and Fitbit[®].

Study Design:

We will use standardized procedures to ensure uniform instructions and support for all subjects for the recruitment, screening, and study entry.

Recruitment:

Mayo Clinic - NCT05199233

Patients with Post-Covid Syndrome will be recruited from the Mayo Clinic Practice. The study staff will inform participants of the study during practice meetings, and if the participants indicate interest, they will connect with research staff and arrange a time to meet to begin the consent process.

Participants will not be reimbursed for their time spent in the study, but all participants will be given the option of keeping the Muse-STM Headband system as well as the Fitbit[®] tracker for continued use post study participation.

Consent and Screen:

Study coordinator will meet with the potential participant who has expressed an interest in participating in the study. The study coordinator will begin by introducing the study details, and after determining that the subject has continued interest in study participation, will move on to the study consent. If the subject chooses to consent, the study coordinator will screen the participant for study entry inclusion/exclusion criteria.

Once a subject meets all entry criteria, the post-covid phenotype, as designated by the Post-Covid Clinic staff, will be recorded and the subject will begin study participation. At this point, they will be asked to complete the study surveys/questionnaires. Finally, a POCUS will be performed during this first face to face visit if one has not been completed clinically in the previous 2 weeks.

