Please note: Patients must have access to an iOS or Android capable device to take part in this study in order to interact with the Muse-STM Headband system.

Treatment phase:

During the first three months of study, participants will be asked to complete the online study intervention using the Muse-STM headband. Participants will be contacted via telephone and online (REDCap) for study visits at day 2, 30 and 60. At day 90, they will be asked to return to the clinic for an in-person visit (telephone and online will be alternatives).

Study Follow-Up Visits:

The study will consist of a 6-month visit post baseline (3-month post end of intervention). Participants will be asked to complete an in-person visit, if possible (telephone and online will be the alternative), which will include a second POCUS exam.

Subject Information

Target accrual: We plan to recruit 80 patients diagnosed with Post-Covid Syndrome at Mayo Clinic with the intent of enrolling 60 to study.

Subject population: A total of 60 patients diagnosed with Post-Covid Syndrome at Mayo Clinic who meet the following study criteria:

Inclusion Criteria:

- 1. 18 years of age or older at time of consent
- 2. Identified with Post-Covid Syndrome (PASC) at Mayo Clinic Rochester:

Wearable for LC

PIs: [name]; [name], PhD

Mayo Clinic - NCT05199233

- 3. Not pregnant by subject self-report at time of consent
- 4. Have the ability to provide informed consent
- 5. Have the ability to complete all aspects of this trial
- 6. Have access to an iPhone, iPad, or Android device
- 7. Have no contraindicating comorbid health condition which would interfere with the proper use of the Muse-STM system, as determined by the clinical investigators

Exclusion Criteria:

- 1. Used an investigational drug within the past 30 days
- 2. Anyone that is not on a stable dose of medication for anxiety, depression or sleep
- 3. Currently (within the past 3 weeks) been practicing mindfulness training on a weekly/regular basis
- 4. Currently (within 3 weeks) has been enrolled in another clinical or research program which intervenes on the patients' QOL, or stress
- 5. An unstable medical or mental health condition as determined by the physician investigator

Data Analysis

Data Analysis Plan:

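### Both anxiety-type measures are momentary, and no rule sets survey timing relative to a Muse-S session, so passing post-session calm can enter the scores

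*Combined protocol and SAP*

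**What the plan says.** - **Anxiety (Assessments).** The STAI-Y1 is a 20-item form on which "the participant indicates how they feel in the moment (1 = not at all to 4 = very much so".
- **Emotional Distress (Assessments).** The source form asks about seven days. Here, "we will reword the question to focus on the current time ('now".
- **When and how.** The schedule table collects both forms at days 0, 30, 60, 90 and 180. Days 30 and 60 are phone or email contacts. The Treatment phase section adds: "At day 90, they will be asked to return to the clinic for an in-person visit (telephone and online will be alternatives". Day 180 is likewise in person where possible.
- **Data Collection.** "Subjects will have the options of completing study surveys/questionnaires online via email link to REDCap prior to study visit". The fallback is an iPad in clinic or a telephone interview.
- **Baseline.** Once entry criteria are met, Consent and Screen says: "At this point, they will be asked to complete the study surveys/questionnaires". The Intervention section places the first practice session at this visit too, "which will be completed during the baseline visit with the study coordinator". Only the quality-of-life form (LASA) has a stated order: "This data will be collected at screen (prior to any treatment".
- **Use of the data.** Primary aim 2 relates device use to self-reported scores that include anxiety, and the secondary outcomes are "change in quality of life (QOL), stress, anxiety, and cognition, score over time". The Data Analysis Plan takes number of sessions as the exposure in mixed models. It does not list anxiety or distress among the modelled outcomes, and it treats every analysis as exploratory.
- **Session times.** Under Server Data, the team can see when each session took place and how long it lasted.

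**The concern.** A score for how someone feels right now depends on what they have just been doing, and the intervention is designed to produce calm. If a participant practises and then opens the survey link, the answer reflects the last half hour as well as the past month. The chance of this rises with the number of sessions, which is the exposure in the planned association. The artefact can therefore look like the hypothesised dose-response. There is one group, so no comparison arm would cancel it.

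The rewording of the distress form removes the one anxiety-type recall that covered a longer period, so neither measure can act as a check on the other. The plan does not separate survey from session, record the interval between them, or adjust for it. What is at stake is how to interpret the change in anxiety and distress and their association with use.

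**Working it through.** **Step 1. Where it can arise.**

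| Day | Survey route | Exposure to a session effect |
|---|---|---|
| 0 | Face to face; order against the first session not written for STAI-Y1 or distress | A score taken after the session would lower baseline anxiety |
| 30, 60 | Phone or email, with the link available beforehand | Clearest |
| 90 | In person requested, remote as alternative; the link can still be used before the visit | Possible |
| 180 | In person if possible; no Muse-S use marked in the schedule | Only with continued voluntary use |

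Stress (PSS, described as global life stress) and sleep (prior 7 days) are less exposed.

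**Step 2. No plan figure to reproduce.** The protocol gives no expected anxiety effect, standard deviation (SD) or power. Everything below is illustrative. From the documents: 60 participants, at least 4 sessions a week (Methods) or daily practice (Intervention), and a STAI-Y1 span of 20 × (4 − 1) = 60 points. Assumed: a 16-hour waking day, calm lasting h hours, and an acute drop of 8 points.

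**Step 3. Association with use, random survey timing.** The share answering within h hours of a session is s × h / (7 × 16), with s sessions a week. For h = 2:

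- daily: 7 × 2 / 112 = 0.125
- four a week: 4 × 2 / 112 = 0.071
- weekly: 1 × 2 / 112 = 0.018

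Spurious differences:

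- daily against weekly: (0.125 − 0.018) × 8 = 0.9 points
- daily against four a week: (0.125 − 0.071) × 8 = 0.4 points

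The result scales with h. Daily against weekly is (7 − 1) × 1 / 112 × 8 = 0.4 points at 1 hour and (7 − 1) × 4 / 112 × 8 = 1.7 points at 4 hours.

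**Step 4. Association with use, surveys clustered after sessions.** If 50% of daily and 10% of weekly users answer straight after a session, the difference is (0.50 − 0.10) × 8 = 3.2 points.

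**Step 5. Mean change.** Let p be the share of follow-up surveys answered in the post-session state and d the transient effect in SDs of change. With no lasting change, the false mean change is p × d. The 95% confidence interval half-width is 1.96 / √60 = 0.25 SD if all 60 contribute.

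| Scenario | p | d | False change (SD) | Chance the interval excludes zero |
|---|---|---|---|---|
| Random timing, 4 a week, 1 h | 0.036 | 0.5 | 0.02 | 5% |
| Random timing, daily, 4 h | 0.25 | 0.5 | 0.13 | 16% |
| Half the surveys follow a session | 0.5 | 0.5 | 0.25 | 49% |
| All follow a session | 1 | 0.5 | 0.50 | 97% |
| All follow a session, weaker effect | 1 | 0.2 | 0.20 | 34% |

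**Step 6. Direction.** If a share p0 of baselines also follows a session, the false improvement becomes (p − p0) × d. It turns into a false worsening when p0 exceeds p.

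**The case against.** The case on the other side is substantial.

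- **Nothing says surveys follow sessions.** A reader might infer that passing calm is recorded as lasting change. The documents do not support that: they promise only change in score over time, and they describe state anxiety as temporary. They also do not say that the survey is answered on the device that runs the Muse app. What can be said is that transient calm can enter the score.
- **Follow-up is not all at home.** Days 90 and 180 are requested in person. This stands, although the emailed link is not limited to remote visits.
- **A pre-practice baseline is not established.** Consent and Screen suggests surveys come first, but the explicit statement covers only the LASA. This stands, and it leaves the direction of bias open.
- **The magnitudes are assumed.** They are, and random timing may overstate exposure, because some sessions are go-to-sleep content meant for use in bed.
- **Little inference depends on it.** Adherence is the primary outcome, no model is named for anxiety or distress, and all analyses are exploratory. This limits the consequences. However, the exploratory label is given because of the number of outcomes and does not address bias, and anxiety remains in primary aim 2 and the secondary outcomes.

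**Conclusion.** The concern holds as a gap in survey timing for two momentary measures. Post-session calm can enter the STAI-Y1 and Emotional Distress scores, more often in frequent users, and can bias both the mean change and the association with use. An unfixed order at the baseline visit can bias change the other way.

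The size is unknown. With random timing, an 8-point drop and 2 hours of calm, it is 0.9 points or less on a 60-point span. It becomes material only if surveys cluster after sessions: 3.2 points in the usage contrast, or a false mean change equal to the confidence interval half-width when half the surveys do so and d = 0.5 SD. The plan neither prevents that case nor would reveal it. A demonstrated bias is not shown. The point is best treated as a cheap improvement to an exploratory outcome.

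**What to change.** 1. **Visit 1.** State that STAI-Y1 and Emotional Distress are completed before the Muse-S demonstration and first session.
2. **Follow-up.** Add one line to the REDCap email asking participants to complete these two forms before that day's session.
3. **Analysis.** Derive time since last session from survey completion times (assuming REDCap keeps them; the protocol does not say) and the Muse session times, linked by study ID. Add it as a covariate in a sensitivity analysis of the anxiety and distress results. It will be correlated with number of sessions, so report estimates with and without it.
4. **Secondary check only.** Repeat the results without scores given soon after a session, for example within 2 hours. This should not be the main remedy, because it removes frequent users selectively and can itself distort the usage association.

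The cost is one ordering rule, one added instruction and a time-stamp merge. For surveys already collected, items 3 and 4 remain possible if completion times were kept. The session times must be extracted before the end-of-study deletion of cloud data described under Server Data.

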- Cognitive Testing: The Cambridge Brain Science (CBS) web-based tests were developed in the laboratory of [name], Canada Excellence Research Chair in Cognitive Neuroscience and Imaging (owenlab.org), over the course of his 25-year career. The tests are self-administered, do not require supervision, and effectively assess aspects of cognition including reasoning, memory, attention and verbal ability. Over 300 scientific studies have been run to date using the CBS tests, yielding numerous publications in leading academic journals²⁴⁻²⁷. The tests have been validated in studies of patients, brain imaging studies of healthy volunteers and in several large-scale public studies involving tens of thousands of volunteers. They have proven to be efficient and sensitive measures of cognitive performance and can be used to consistently monitor participants and patients due to the unlimited versions of problem sets within each task. The 12 tasks (*see CBS Task Overview.pdf) can be customized to use specific tasks if a shortened assessment is required for research. A custom 3-task assessment would take approximately 10 minutes and for the purposes of this study, we would recommend the use of the following tasks:
 - 1) **Double Trouble** 90 seconds (*measure of Response Inhibition*) Version of the Stroop task. It is a "double" version in which there can be up to two incongruities (the top word and the bottom words), so is a little more difficult than other versions and has been sensitive to a range of interventions known to improve attention, response inhibition, or cognition in general. Response times and accuracy can be separately calculated for each difficulty level (congruent /incongruent / double incongruent), in addition to an overall score.
 - 2) Feature Match 90 seconds (*measure of Attention*) Version of a "spot the difference" game. It uses areas of the brain involved in tuning attention and requires both fast response time and accuracy to get a good score.
 - 3) **Monkey Ladder** (measure of Memory)- Sets of numbered squares are displayed on a screen at random locations. After a set time the numbers disappear leaving blank squares. The participant must respond by clicking the squares in ascending numerical sequence. Difficulty is increased or

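### In a single-arm study the scored CBS baseline is the first study attempt, so change in CBS scores may include a practice gain that cannot be told apart from a device effect

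*Combined protocol and SAP*

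**What the plan says.** The study has one arm: "All study participants will receive the Muse"-S headband (Methods). The enrolment target is 60: "We plan to recruit 80 patients diagnosed with Post-Covid Syndrome at Mayo Clinic with the intent of enrolling 60 to study" (Target accrual).

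The schedule table in Methods places "CBS Cognitive Tests" at visits 1, 5 and 6, which are days 0, 90 and 180. No earlier or practice administration is listed there or under Cognitive Testing. That section selects three web-based tasks taking about 10 minutes in all: Double Trouble (90 seconds), Feature Match (90 seconds, scored on speed and accuracy) and Monkey Ladder. They are self-administered and unsupervised. The reason given for relying on repeated scores is that the tests "can be used to consistently monitor participants and patients due to the unlimited versions of problem sets within each task".

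Visit 1 is face to face. Visits 5 and 6 are listed as "Face to Face/ Phone/ Email". For day 90, Treatment phase says "they will be asked to return to the clinic for an in-person visit (telephone and online will be alternatives"; Study Follow-Up Visits says much the same for day 180. Nothing fixes which device is used for CBS, where it is taken, or where it falls within a visit. The first Muse-S session also takes place at the baseline visit (Intervention).

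The secondary outcomes include "change in quality of life (QOL), stress, anxiety, and cognition, score over time". The Data Analysis Plan analyses cognitive testing with mixed models similar to the one for stress and sleep. The predictor named there is number of sessions, and no visit or time term is named. Results are to be given as estimates with 95% confidence intervals, and all analyses are called exploratory.

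**The concern.** Fresh problem sets answer only one of the two ways in which a repeated test can improve. They stop a participant remembering a particular item. They do not stop a participant from knowing, the second time, what the task asks, how the screen responds and which strategy works. In a 90-second test a slow start costs score directly. Here the slow start, if there is one, falls entirely in the baseline score.

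In a randomised trial a control arm would carry the same retest gain and the comparison would cancel it. This study has no such arm, so pre-post CBS change is the sum of any device effect, any retest gain, natural change in the condition, and any effect of testing in a different place or on a different device. What is at stake is how the cognition result is read: an inert device could be reported with a positive CBS change and an interval that excludes zero.

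The sessions model may carry the same problem. If sessions are counted cumulatively, they are zero at the first attempt and high at the later ones, so a gain caused by repetition lines up with use of the device.

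**Working it through.** The documents give no effect size, SD, retest correlation or practice gain for CBS, and no justification of the sample size. There is no planned figure to reproduce. The following is an illustration with no true device effect.

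**Inputs from the plan:** 60 participants; tests at days 0, 90 and 180; 95% intervals; target use of at least 4 sessions a week for 12 weeks, 4 × 12 = 48 sessions.

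**Assumed inputs:** retest correlation r = 0.7 (range 0.5 to 0.8); retest gain g from 0 to 0.4 baseline SD; equal SD at each visit; 20% loss as an alternative, 60 × 0.8 = 48.

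**1. Mean change from baseline.**
SE = √(2(1 − r)/n) in SD units. With r = 0.7 and n = 60: √(0.6/60) = 0.100.
95% half-width = 1.96 × 0.100 = 0.196 SD.
Chance that the interval lies wholly above zero = Φ(g/SE − 1.96). For g = 0.2: Φ(2.00 − 1.96) = Φ(0.04) = 0.516.

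| Retest gain (SD) | n = 60, r = 0.7 | n = 48, r = 0.7 |
|---|---|---|
| 0 | 2.5% | 2.5% |
| 0.1 | 17% | 14% |
| 0.2 | 52% | 43% |
| 0.3 | 85% | 77% |
| 0.4 | 98% | 95% |

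At g = 0.3 the figure runs from 64% (r = 0.5) to 96% (r = 0.8) for n = 60, and from 55% to 91% for n = 48.

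**2. Sessions model.** Simulation with 1,000 runs per setting: 60 participants, three visits, a random intercept, r = 0.7. Cumulative sessions are 0 at baseline, then have mean 48 and SD 20 (assumed). The same gain applies at days 90 and 180. The entry is the share of runs showing a positive sessions association whose 95% interval excludes zero.

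| Retest gain (SD) | No visit term | Categorical visit term |
|---|---|---|
| 0 | 3% | 2% |
| 0.1 | 20% | 2% |
| 0.2 | 53% | 2% |
| 0.3 | 90% | 2% |
| 0.4 | 99% | 2% |

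At g = 0.3 without a visit term, the result is 91% for a session SD of 10 and 80% for 30. With the visit term it is about 3% in both cases. The visit term absorbs a gain that is common to everyone. It does not absorb a gain that differs with amount of use.

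**The case against.** Several things can be said for the plan. The size of the gain is assumed. Over a 90-day gap it could be near zero, and at 0 to 0.1 SD the chance of a misleading interval is only 2.5% to 17%. CBS is one of several secondary measures, the primary outcome is adherence, neither secondary hypothesis under Endpoints mentions cognition, and everything is labelled exploratory. The CBS task overview that the protocol cites is not among the documents and may describe practice trials. The mixed model could include visit, which would protect the sessions association. All of this stands as a limit on size and importance. None of it separates practice from device effect in the pre-post change, and the exploratory label does not remove bias from the estimates that will be reported.

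A reader might go further and infer that later testing is easier than baseline testing, so that conditions also push the change upward. The documents do not support that. The schedule repeats the same questionnaires at visits 5 and 6, and day 180 adds a satisfaction survey and end-of-study forms. Consent and Screen does say "Finally, a POCUS will be performed during this first face to face visit", but only if none was done clinically in the previous two weeks, and an in-person day 180 visit includes a second one. The length of the baseline visit and the place of CBS within it are not stated. In-person attendance is preferred later, and home testing could lower scores through distraction or a different screen as readily as raise them.

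A reader might also infer that CBS serves primary aim 2, because that aim names cognition. The aim specifies self-assessment surveys, which fits the PROMIS cognitive form and not a performance test.

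**Conclusion.** The point holds as a possible bias that the design cannot detect or remove. The scored CBS baseline is the first study attempt, the only stated safeguard does not address task learning, and there is no control arm. With n = 60 and r = 0.7, an assumed gain of 0.2 to 0.3 SD would give an interval wholly above zero 52% to 85% of the time with no device effect, and a cumulative-sessions model without a visit term would be misled about as often (53% to 90%). These figures rest on assumed gains and correlations. The documents do not show that a gain will occur, only that one could not be distinguished.

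The unfixed device, place and order of testing are an uncontrolled difference of unknown direction, and no sign should be attached to it. The day 90 to 180 change should not be treated as a clean estimate free of device effect either: treatment has ended, but participants keep the headband and may go on using it.

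**What to change.** 1. At visit 1, give one unscored run of the three CBS tasks, then the scored baseline run.
2. Take the scored run before the first Muse-S session. Have each participant use the same device at days 0, 90 and 180, and record where each test was taken.
3. Include visit as a categorical term in the CBS mixed model, so that a retest gain common to all is not attributed to number of sessions.
4. Report within-group CBS change as possibly including practice, and not as an effect of the device.

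The cost is about 10 more minutes at an already full baseline visit, plus wording on order and device. The apparent improvement is likely to be smaller, because part of any learning moves ahead of the baseline. One practice run reduces learning but does not eliminate it, so item 4 is needed even if item 1 is adopted. With the visit term, the sessions estimate rests on differences in use between participants and will be less precise. The visit term does not correct the change-over-time estimate itself. If enrolment has already begun, items 3 and 4 need no new data.
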